### 5.2.2 Stopping Initial Treatment with Plasma Exchange and Corticosteroids.

When the criteria for Treatment Response are met (platelet count  $\geq 150,000/\mu\text{L}$  for 2 consecutive days), plasma exchange is to be discontinued and tapering of corticosteroid initiated. Steroid tapering may be accelerated at the discretion of the clinician.

**Table 1: Suggested Prednisone Taper Schedule**

Week after stopping PE	Dose of Prednisone (mg/kg)
1	0.5 per day
2	0.25 per day
3	0.375 every other day
4	0.25 every other day
5	0.125 every other day
6	0.0625 every other day
7	stop

### 5.2.3 Treatment of Exacerbation with Plasma Exchange and Corticosteroids.

If a subject achieves a Treatment Response by day 28 and subsequently has a platelet count (confirmed by a repeat count)  $\leq 120,000/\mu\text{L}$  within 30 days after stopping plasma exchange, then plasma exchange and corticosteroid treatments are to be restarted as described under **section 5.2.1**. The confirmatory platelet count must be a discrete collection drawn 1 to 24 hours after the first collection.

### 5.2.4 Stopping Treatment of Exacerbation with Plasma Exchange and Corticosteroids

After an early exacerbation plasma exchange is to be stopped and corticosteroids tapered when the subject has a platelet count  $\geq 150,000/\mu\text{L}$  on 3 consecutive days.

### 5.2.5 Treatment of Refractory TTP

The subject will be considered to have Refractory TTP if they do not have a Treatment Response by day 28, or do not have a Durable Treatment Response by day 60. The treatment of Refractory TTP will include resuming plasma exchange and corticosteroids. Additional salvage therapy is at the physician's discretion and can include full dose rituximab  $375 \text{ mg/m}^2$  weekly for 4 doses. Patient with Refractory TTP will be followed for 2 years with laboratory monitoring.

### 5.2.6 Treatment of Relapsed TTP

Recurring TTP  $>30$  days after Treatment Response is considered to be Relapsed TTP. The treatment of Relapsed TTP will include resuming plasma exchange and corticosteroids. Additional salvage therapy is at the physician's discretion and can include full dose rituximab  $375 \text{ mg/m}^2$  weekly for 4 doses. Patients with Relapsed TTP will be followed for 2 years with laboratory monitoring.

## 5.3 Non-Protocol Treatments

The following medications and other treatments, which can influence the course of TTP, will be considered protocol violations and secondary endpoints if they are given after enrollment.

- 1) Immunosuppresses/cytotoxic agents, including:

- a. Cyclophosphamide
- b. Azathioprine
- c. Vincristine
- d. High dose corticosteroids (>1.5 mg/kg)

2) Calcineurin inhibitors, including:

- a. Cyclosporine A (brands - Sandimmune, Gengraf, Neoral)
- b. Tacrolimus (FK506) (brand - Prograf)
- c. Sirolimus (brand - Rapamune)

3) Anti-platelet agents:

Aspirin, ticlopidine, dipyridamole, NSAIDs, clopidogrel, and other anti-platelet agents may not be given for treatment of TTP per se, but may be administered when indicated for other conditions.

4) Cytokines/growth factors and megakaryocyte simulating drugs, including:

- a. Oprelvekin (IL-11) (Brand- Neumega)

5) Splenectomy

6) Staphylococcal protein A column treatment

7) Intravenous immunoglobulin (IVIG)

## 6. ASSESSMENT

### 6.1 Schedule of Measurements: Refer to Table 2 for Panel descriptions

#### 6.1.1. Pre-Screening

Screening logs will be maintained to track the enrollment status of all patients for participation.

#### 6.1.2 Screening

- 1) Infectious disease testing
  - a. Anti-HIV
  - b. HBsAg, Anti-HBc
- 2) Pregnancy test (serum  $\beta$ -HCG)

#### 6.1.3 Baseline (Table 3)

After evaluation for eligibility, the following measurements will be taken at baseline. Data collected for baseline measurements are to be abstracted from the subject's medical record using the earliest information after admission for TTP. If a laboratory test is not included in the subject's record, it is to be obtained either by using extra serum or plasma collected prior to the first plasma exchange and retained in the clinical laboratory for possible clinical needs, or from initial waste plasma from the first plasma exchange.

1) Demographic and Medical History

- Weight and height
- Gender
- Ethnic origin
- Race
- History of TTP

- Date of onset of symptoms
- Date of first plasma exchange
- Previous plasma infusion prior to enrollment in study during this admission
- Past Medical History including: (see case report form for complete list)
  - Autoimmune disease (SLE, other)
  - Prior thrombotic disease (CVA, MI, DVT, Other)
  - Diabetes (Diet Controlled, Oral Antiglycemics, Insulin)
  - Hypertension (Medication Yes/No)

2) Surveillance panel

3) Peripheral smear

4) Coagulation panel

5) Reticulocyte count

6) Chemistry panel

7) Expanded chemistry panel

8) Other Laboratory

- DAT
- Serum IgG, IgM, and IgA
- Urinalysis with microscopic examination

9) ADAMTS13 activity and antibody (plasma samples will be sent to the Blood Center of Wisconsin and [name])

10) Samples for repository (drawn prior to any plasma exchange or rituximab treatment)

- Serum
- Citrated plasma
- Lithium-heparin plasma
- Packed cells

11) Assessment

- Documentation of clinical status on Baseline Visit CRF
- Documentation of medications on Concomitant Medications CRF
- Plasma Exchange log – for all plasma exchanges since admission

#### **6.1.4 During Plasma Exchange (Table 3)**

- 1) Surveillance panel – a minimum of one per day
- 2) Chemistry Panel- one per day
- 3) ADAMTS13 activity and antibody- collect at least once between 9-13 days after the day of the first plasma exchange, and at least weekly thereafter if the patient is receiving plasma exchange
- 4) Assessment
  - Documentation of clinical status on Follow-Up During Plasma Exchange CRF
  - Concomitant Medication Log, if changes have occurred
  - Plasma Exchange log

#### **6.1.5 After Plasma Exchange is stopped (Table 4)**

- 1) First month
  - Surveillance panel – one per week  $\pm$  2 days
  - Chemistry panel – one per week  $\pm$  2 days
  - ADAMTS13 activity and antibody – on day 7  $\pm$  2 days and day 30  $\pm$  7 days after plasma exchange is stopped
  - Peripheral smear – on day 7  $\pm$  2 days after plasma exchange is stopped
  - Clinical status (Follow-Up Post-PE CRF) and Concomitant Medication Log – one per week  $\pm$  2 days
- 2) Months 1 to 3
  - Surveillance panel – one per month  $\pm$  7 days
  - Chemistry panel – one per month  $\pm$  7 days
  - ADAMTS 13 activity and antibody – one at 3 months  $\pm$  7 days after plasma exchange is stopped
  - Clinical status (Follow-Up Post-PE CRF) and Concomitant Medication Log – one per month  $\pm$  7 days
- 3) Months 4 to 24
  - Surveillance panel – every 3 months for one year after plasma exchange is stopped  $\pm$  14 days
  - Chemistry Panel – one year after plasma exchange is stopped  $\pm$  14 days
  - ADAMTS13 activity and antibody – every 3 months  $\pm$  14 days
  - Clinical status (Follow-Up Post-PE CRF) and Concomitant Medication Log – every 3 months  $\pm$  14 days

#### **6.1.6 After Exacerbation and until plasma exchange is stopped (Table 3)**

- 1) Surveillance Panel – one per day
- 2) Chemistry Panel – one per day
- 3) Coagulation – one during the first day after exacerbation is diagnosed
- 4) Direct Antiglobulin Test – one during the first day after exacerbation is diagnosed
- 5) Peripheral smear – one during first day after exacerbation is diagnosed
- 6) ADAMTS 13 activity and antibody – one during the first day after exacerbation is diagnosed, one between 9-13 days later, and then weekly  $\pm$  2 days if the patient is still on plasma exchange.
- 7) Documentation of clinical status (Follow-Up During Plasma Exchange CRF) and Concomitant Medication log (if changes have occurred)
- 8) Plasma exchange log – one per day

#### **6.1.7 Refractory TTP (Table 5)**

- 1) ADAMTS13 activity and antibody – during the first day after Refractory TTP is diagnosed and then at least every 3 months for 2 years thereafter  $\pm$  14 days
- 2) Serum IgG, IgM, IgA – 1 year after Refractory TTP is diagnosed  $\pm$  14 days
- 3) Clinical status and medication log – every 3 months for 2 years  $\pm$  14 days
- 4) If patient receives standard dose of rituximab as a salvage therapy, the B lymphocyte and rituximab level will be measured based on schedules described in section 6.1.9 and table 6.

#### **6.1.8 Relapsed TTP until the plasma exchange is stopped (Table 3)**

- 1) Surveillance Panel – every day
- 2) Chemistry Panel – every day
- 3) ADAMTS13 activity and antibody – one during the first day after relapse is diagnosed, one 9-13 days later, and then weekly  $\pm$  2 days if the patient is still on plasma exchange.
- 4) Direct Antiglobulin Test – one during the first day after relapse is diagnosed
- 5) Peripheral Smear – one during the first day after relapse is diagnosed
- 6) Clinical Status and Medication Log – every day

#### **6.1.9 B Lymphocyte Levels**

Collect B lymphocyte samples at the following time points. The samples will be collected prior to subject receiving that day's plasma exchange and rituximab, if applicable. Samples will be sent to a central lab for testing.

- Prior to any rituximab infusion
- 3 months ( $\pm$  7 days) after the first plasma exchange
- Six months ( $\pm$  14 days) after the first plasma exchange
- Nine months ( $\pm$  14 days) after the first plasma exchange
- Twelve months ( $\pm$  14 days) after the first plasma exchange

#### **6.1.10 Schedule for measurements of rituximab level**

- As described in Table 6

**Table 2: Panel Descriptions**

Panel Name	Tests in the panel	Amount of sample and tube
Surveillance panel	CBC LDH	5.0 ml purple-top EDTA 0.3 plasma, green top
Peripheral smear	Description of smear by hematologist or hematopathologist.	Use EDTA from surveillance panel
Coagulation lab	INR, PTT, fibrinogen, D-Dimer	5.0 ml blue-top citrate
Chemistry panel	BUN, Creatinine	0.5 ml plasma, green top
Expanded chemistry panel	CPK, ALT, AST, Bilirubin (total and direct)	0.5 ml plasma, green top
Infectious disease testing	Anti-HIV, HBsAg, HBc-Antibody	HIV:10 ml 1 ml serum, red top
Pregnancy test	Serum β-HCG	0.5 ml plasma, green top
ADAMTS13 activity and antibody; plasma Li-heparin		5 ml green top
Direct Antiglobulin Test		5 ml purple-top EDTA
Serum IgG, IgM and IgA		3 ml serum, red top
B lymphocyte		5 ml EDTA tube
Rituximab Level (PK)		5 ml red/gray top
Reticulocyte count		5.0 ml purple-top EDTA

**Table 3: Schedule of Measurements Until Plasma Exchange (PE) is Stopped for Treatment Response**

	Baseline	During PE
Assessment		
Demographic and Medical History	X	
Clinical Status Log	X	One per day
Medication log	X	One per day
PE log		Every PE
Laboratory		
Surveillance Panel	X	One per day
Coagulation panel	X	
Chemistry Panel	X	One per day
Pregnancy Test (screening)		
Infectious disease testing (screening)		
ADAMTS13 activity and ADAMTS13 antibody	X	Day 10 -14, and weekly thereafter if the patient is receiving plasma exchange
Direct Antiglobulin Test	X	
Peripheral smear	X	On first day of PE
Serum IgG, IgM and IgA	X	

**Table 4: Schedule of Measurements After Plasma Exchange (PE) is Stopped for Treatment Response**

	First 30 days of no PE	Months 1 to 3	4 Months to 2 years
Assessment			
Clinical status	1 per week $\pm$ 2 days	1 per month $\pm$ 7 days	Every 3 months for 2 years $\pm$ 14 days
Medication log	1 per week $\pm$ 2 days	1 per month $\pm$ 7 days	Every 3 months for 2 years $\pm$ 14 days
Laboratory			
Surveillance Panel	1 per week $\pm$ 2 days	1 per month $\pm$ 7 days	Every 3 months for 1 year after first PE $\pm$ 14 days
Chemistry Panel	1 per week $\pm$ 2 days	1 per month $\pm$ 7 days	1 year after first PE $\pm$ 14 days
ADAMTS13 activity and antibody	Day 7 $\pm$ 2 days and day 30 $\pm$ 7 days	1 at month 3 $\pm$ 14 days	Every 3 months for 2 years after first PE $\pm$ 14 days
Peripheral smear	Day 7 $\pm$ 2 days		
Serum IgG, IgM and IgA			One year after first PE $\pm$ 14 days

**Table 5: Schedule of Measurements When Refractory TTP is diagnosed**

Assessment	Frequency
Clinical status	4 times per year (quarterly) after the first PE for 2 years $\pm$ 14 days
Medication log	After the first PE for 2 years $\pm$ 14 days
Laboratory	
Serum IgG, IgM, IgA	1 year after the first PE $\pm$ 14 days
ADAMTS13 activity and antibody	On the day Refractory TTP is diagnosed Then every 3 months up for 2 years $\pm$ 14 days

**Table 6: Schedule for Measurements of Rituximab Level**

Event	Samples
First rituximab infusion	Within 30 minutes before starting the infusion
	Within 30 minutes after the end of the infusion
	13-25 hours after the end of infusion, and before the next PE
	Within 30 minutes after the first PE following the rituximab infusion
	Within 30 minutes before the second PE following the rituximab infusion
Second rituximab infusion	Within 30 minutes before starting the infusion
Third rituximab infusion	Within 30 minutes before starting the infusion
Fourth rituximab infusion	Within 30 minutes before starting the infusion
	Within 30 minutes after the end of the infusion
Follow up	3 months after the last infusion of rituximab $\pm$ 14 days
	6 months after the last infusion of rituximab $\pm$ 14 days
	12 months after the last infusion of rituximab $\pm$ 14 days

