#### 1.2.2 Laboratory Objectives

- Assess the relationship of ADAMTS13 enzyme activity and ADAMTS13 autoantibody titer to indicators of disease activity including:
  - Primary and secondary clinical endpoints
  - Platelet count
  - LDH
  - B cell depletion and recovery
- Assess the relationship of rituximab levels to the extent and duration of B cell depletion
- Describe the effect of plasma exchange on rituximab levels

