### **5.1.4 Administration While on Plasma Exchange**

The rituximab infusion is to be given immediately after plasma exchange. The next plasma exchange is to be performed as late as possible in order to maximize exposure to rituximab. At least a 20-hour time interval between rituximab and plasma exchange is the goal. Plasma exchange is not to be performed sooner than 12 hours after the end of a rituximab infusion.

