### **8. CRITERIA FOR REMOVAL FROM PROTOCOL THERAPY AND OFF STUDY**

#### **8.1. Criteria for removal from Protocol therapy with adjuvant low dose rituximab**

- 1) Salvage Therapy before all four doses of rituximab are administered
- 2) Two or more exacerbations in the first 30 days after enrollment
- 3) Plasma Exchange is performed sooner than 12 hours after the end of rituximab infusion

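### The rituximab sample before the first post-infusion exchange has no valid time if exchange starts at 12 to 13 hours, and for later starts it is not tied to the exchange

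*Combined protocol and SAP*

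**What the plan says.** Section 1.2.2 lists as a laboratory objective: "Describe the effect of plasma exchange on rituximab levels". Table 6 serves it with five samples around the first infusion. Three of them matter here:

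- before the first exchange after the infusion: "13-25 hours after the end of infusion, and before the next PE";
- after that exchange: within 30 minutes of it;
- before the following exchange: "Within 30 minutes before the second PE following the rituximab infusion".

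Table 6 also takes a level at the end of the infusion: "Within 30 minutes after the end of the infusion".

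Section 5.1.4 sets when exchange may follow: "Plasma exchange is not to be performed sooner than 12 hours after the end of a rituximab infusion". It adds a target, "At least a 20-hour time interval between rituximab and plasma exchange is the goal", and a direction, "The next plasma exchange is to be performed as late as possible in order to maximize exposure to rituximab". Section 8.1 makes it a ground for removal from protocol therapy if "Plasma Exchange is performed sooner than 12 hours after the end of rituximab infusion".

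Section 9.2 plans to analyse rituximab levels as stratified categories with Cochran-Mantel-Haenszel statistics. It describes no calculation of removal per exchange.

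**The concern.** The effect of an exchange on the drug level is the change from just before to just after it. Table 6 times the post-exchange sample, and the sample before the second exchange, by the exchange itself. It times the sample before the first exchange by the infusion, and sets no limit on how long before exchange it may be drawn.

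Two things follow. The earliest sampling time (13 hours) is one hour later than the earliest permitted exchange (12 hours), so some exchanges that comply with the protocol leave no time for a compliant sample. For later exchanges, the interval between sample and exchange can differ from patient to patient, and any natural decline in it would look like removal.

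What is at stake is a descriptive laboratory objective. Table 6 has no sample timed after the second exchange and none timed to exchange after later infusions, so each patient has one scheduled bracket around an exchange. Section 9.1 plans 20 patients. A lost or poorly timed sample is not replaced elsewhere in the schedule.

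**Working it through.** The plan states no figure to reproduce here. The check has two parts.

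**1. Is there a valid sampling time, and how far from exchange can it be?**

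Inputs: sampling window of 13 to 25 hours and before exchange (Table 6); exchange permitted from 12 hours, with a goal of 20 hours or more (section 5.1.4); removal from protocol therapy only below 12 hours (section 8.1).

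Let T be the start of exchange in hours after the end of infusion. The sample must fall between 13 and the smaller of 25 and T. The longest gap to exchange is T - 13; the shortest is the larger of 0 and T - 25.

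| Exchange start T (h) | Valid sampling time (h) | Gap to exchange (h) |
|---|---|---|
| 12, 12.5, 13 | none | - |
| 13.5 | 13 to 13.5 | 0 to 0.5 |
| 16 | 13 to 16 | 0 to 3 |
| 20 | 13 to 20 | 0 to 7 |
| 24 | 13 to 24 | 0 to 11 |
| 25 | 13 to 25 | 0 to 12 |
| 28 | 13 to 25 | 3 to 15 |

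This part needs no assumption. The sample is impossible at 12 to 13 hours. A gap is optional above 13 and up to 25 hours, and forced beyond 25 hours.

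**2. How much could the gap matter?**

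The documents give neither a half-life nor a removal fraction, so both are assumed.

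- Decline over a gap g at half-life h: d = 1 - 2^(-g/h).
- Removal by an exchange of 1.5 plasma volumes (the target in section 5.2.1), one-compartment model: r = 1 - exp(-1.5) = 77.7%.
- Apparent removal: 1 - (1 - d)(1 - r).
- Overstatement: apparent removal minus r, which is (1 - r) x d.

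For g = 12 hours:

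| Assumed half-life | Decline d | Apparent removal | Overstatement (points) |
|---|---|---|---|
| 24 h | 29.3% | 84.2% | 6.5 |
| 48 h | 15.9% | 81.2% | 3.6 |
| 72 h | 10.9% | 80.1% | 2.4 |
| 10 days | 3.4% | 78.4% | 0.8 |
| 20 days | 1.7% | 78.1% | 0.4 |

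With exchange at the 20-hour goal the longest gap is 7 hours. The overstatement is then at most 4.1 points (24 h), 1.5 (72 h), 0.4 (10 days) or 0.2 (20 days).

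The result depends on true removal, which is what the objective sets out to learn. If exchange removed only 50% (assumed), a 12-hour gap would add 0.5 x 29.3% = 14.6 points at 24 hours, 0.5 x 10.9% = 5.5 at 72 hours and 0.5 x 3.4% = 1.7 at 10 days.

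With the sample tied to within 30 minutes before exchange, every permitted start has a valid sampling time. Decline in the gap is then at most 1.4% (24-hour half-life), an overstatement of 0.3 points at 77.7% removal.

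**The case against.** The strongest reply is that the plan works if sites follow its intent. Section 5.1.4 sets a 20-hour goal and asks for exchange to be late, so a start at 12 to 13 hours misses the goal by at least 7 hours and may be uncommon; the documents give no frequency. That stands as a limit on how often the sample is lost. It does not remove the mismatch, because such an exchange remains within protocol.

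A reader might infer that whenever the sample is possible, it mixes natural decline with removal. The documents do not support that. A draw minutes before exchange meets Table 6 for any start after 13 and up to 25 hours, so the row permits mixing without building it in.

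A reader might also take the 11 to 29% decline over 12 hours, at half-lives of 72 to 24 hours, as added removal. Decline and removal multiply, so it would be that large only if exchange removed nothing.

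The design also holds some information on decline. The end-of-infusion level gives a slope up to the pre-exchange sample, and the levels after the first and before the second exchange give another. These help only if actual times are recorded and decline is modelled. The documents mention an exchange log but do not say that clock times of samples and exchanges are captured, and section 9.2 plans no such model. A slope from the end of infusion also assumes constant decline.

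It is fair, too, that no before/after subtraction is written down. The bias arises only if the pair is used that way, which is the natural use of it for this objective.

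Finally, the present row gives a roughly one-day level whether or not exchange continues. Replacing it outright would lose the sample in a patient with no further exchange. That stands, and the fix needs a fallback.

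**Conclusion.** The point holds as a minor one. Table 6 and section 5.1.4 do not fit together for exchange starting at 12 to 13 hours, and that follows from the text alone. For later starts the row sets no maximum gap, unlike the adjacent exchange-timed rows. The gap can reach 12 hours for starts up to 25 hours, and beyond that some gap is unavoidable.

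The size of any bias rests on assumed values. For a 12-hour gap and 78% removal it is about 2.4 to 6.5 points at half-lives of 72 to 24 hours, and under 1 point at 10 to 20 days. It is larger if exchange removes less. It affects one descriptive laboratory objective and leaves the primary endpoint untouched.

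**What to change.** Rewrite the one row in Table 6 so that the sample is drawn within 30 minutes before the start of the first exchange after the infusion, with the clock times of sample and exchange recorded. If no further exchange is given, draw it 13 to 25 hours after the end of infusion, as now.

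The number of samples does not change. The small cost is that the post-infusion time of this level will vary with the time of exchange, so it is less uniform as a one-day level for the objective relating rituximab levels to B cell depletion; the recorded times allow for that. The change reconciles the sampling row with section 5.1.4. It concerns sampling time only and takes no view on when exchange should be given.

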## 6.2 Specimen collection procedures

To avoid dilution effects on screening and eligibility tests (especially HBsAg, Anti-HBc antibody,  $\beta$ -HCG and ADAMTS13 antibody measurements) we will screen subjects and obtain samples prior to the first plasma exchange when possible.

If enrollment occurs after plasma exchange has begun, the following alternative sequence of specimen acquisition is to be followed:

We will attempt to utilize extra serum or plasma held for possible clinical needs in the routine clinical laboratory for these tests – provided it meets the laboratory's criteria for HBsAg, Anti HBc, and  $\beta$ -HCG testing.

Otherwise properly procured peripheral blood sample will be obtained for HBsAg, Anti-HBc and  $\beta$ -HCG to confirm clinical eligibility despite plasma exchange(s).

Measurement of HBsAg, Anti-HBc, and  $\beta$ -HCG on undiluted waste plasma (see below) is to be run in parallel.

Directions for obtaining and storing this waste plasma are as follows: After the first 50 mL of plasmapheresis plasma is collected into the waste bag, 50 mL will be diverted into a transfer bag and retained for special studies (pending informed consent of the subject if not already obtained). The remainder of the plasmapheresis plasma will then be run into the waste bag. The transfer bag will be sent to the blood bank or other location and stored at 1-6°C until disposition is determined. Material in this bag will be aliquoted into at least six 5 mL freezer-safe tubes (two of these may be used for HBsAg and  $\beta$ -HCG screening, one may be used for ADAMTS13 activity and antibody, and two may be used for sample repository, if needed), and one 15 mL aliquot. Samples are to be frozen at -80°C. Samples may be initially stored at -20°C in a non-frost-free freezer for a maximum of 30 days. Unless used for screening purposes, the tubes and aliquot will be batched and forwarded to the repository for storage.

- 1) Peripheral Blood smears will be collected for confirmation of microangiopathic changes.
- 2) ADAMTS13 activity and antibody samples
  - 5 ml green top tube (or saved plasma) to yield 2.5 mL of lithium-heparinized plasma. The leftover plasma will be sent to the repository for storage.
- 3) B lymphocyte levels:
  - 5 ml EDTA tube

